### **Sub-Study Endpoint**

1. Radiological changes in CT scan at EOT in the LAI arm compared to multi-drug regimen alone, where appropriate
2. Six-month interval safety assessment for subjects enrolled at sites in Japan

### **Sub-Study Population**

All Japanese subjects at all study sites in Japan will participate in this sub-study once they have IRB/EC approval. The informed consent for this Japan specific CT Scan Sub-Study is included in the informed consent for the main study. All Japanese subjects in Japan will participate in this sub-study. There are no separate inclusion or exclusion criteria for this sub-study.

### **Sub-Study Procedures**

The subject should have a chest CT scan performed (a prior CT scan that was obtained within 6 months prior to Day 1 may be used for Baseline). The first chest CT scan should be performed at Day 1 or up to 14 day after first dose of LAI or multi-drug regimen. Additional CT scans will be obtained at their Months 6, 12, EOT months (if at least 6 months have elapsed since the previous CT scan), and at 18 and 24 months after EOT.

All chest CT scans will be read locally and a description of findings for each scan will be entered into the eCRF page. An overall assessment of improved, worsening, or no change from previous scan will be reported for all scans after the subject's Baseline scan. All chest CT scans must be made available to the Sponsor to be stored as study source documentation.

Protocol Amendment #3 version: 22 February 2016

*This protocol is solely for the purpose of communicating information about the investigational drug between Insmmed Incorporated and study personnel. Information is not to be reproduced, abstracted or used for sharing of information for any other purpose, whatsoever, except with the written permission of Insmmed Incorporated.*

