At Month 8, all non-converters will be discontinued from INS-212 (Section 4.6). All subjects who experienced a relapse or recurrence (Section 4.6) by Month 6 will also be discontinued from INS-212 at their Month 8 visit. These subjects may be eligible to enter a separate open-label study of LAI (Study INS-312), provided all entry criteria have been met for that study.

[figure not shown]
Expectorated sputum (spontaneous or induced e.g., with nebulized hypertonic saline solution as needed) will be collected at Day 1 and every month through Month 6, and at Months 8, 12, at EOT, at 28 days, 3, 6 and 12 (EOS) months off-treatment.

All subjects will come in monthly for routine visits through Month 6, at Months 8, 10, 12, 14, EOT, and at 28 days, 3, 6 and 12 (EOS) months off-treatment. Home Healthcare visits may be available at Months 1, 2, and 5 for sites with IRB/EC approval to conduct Home Healthcare visits, and qualifying subjects who may have difficulty attending clinic visits. (At Months 10 and 14 subjects randomized to LAI will return to the clinical site for drug dispensation, and AE and concomitant medication assessments). Unscheduled visits will occur as needed should subjects' symptoms worsen between visits.

Protocol Amendment #3 version: 22 February 2016

*This protocol is solely for the purpose of communicating information about the investigational drug between Insmid Incorporated and study personnel. Information is not to be reproduced, abstracted or used for sharing of information for any other purpose, whatsoever, except with the written permission of Insmid Incorporated.*

Figure 3-1 Study Design

\*All converters (at least 3 consecutive monthly negative sputum cultures by Month 6) will remain in study for 12 months, starting from the first negative culture that defines culture conversion.

\*All non-converters and subjects who experienced a relapse or recurrence after culture conversion will discontinue the study at Month 8 and may be eligible to enter a separate Open-Label study (INS-312).

Protocol Amendment #3 version: 22 February 2016

*This protocol is solely for the purpose of communicating information about the investigational drug between Insmed Incorporated and study personnel. Information is not to be reproduced, abstracted or used for sharing of information for any other purpose, whatsoever, except with the written permission of Insmed Incorporated.*

Confidential

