INS-212	Screening	TREATMENT PHASE											OFF-TREATMENT PHASE							
		Baseline	Month 1 a	Month 2 a	Month 3	Month 4	Month 5 a	Month 6	Month 8	Month 10	Month 12	Month 14	EOT up to Month 16	28 Day Safety Follow-Up	3 Month Safety Follow-Up	6 Month Safety Follow-Up	EOS (12 Month Safety Follow-Up)			
		(V1)	(V2)	(V3)	(V4)	(V5)	(V6)	(V7)	(V8)	(V9)	(V10)	(V11)	(V12)	(V13)	(V14)	(V15)	(V16)	(V17)		
Visit Window	Approximately -98 to -70 (10-14 weeks) b	Day 1	(±3)	(±3)	(±3)	(±3)	(±3)	(±3)	(±3)	(±3)	(±3)	(±3)	(±5)	(±5)	(±5)	(±5)	(±5)	(±7)	(±7)	(±7)
Send sputum collection containers home	X	X	X	X	X	X	X	X	X	X	X	X	–	X	–	X	X	X	X	–
Administer study drug at site	–	X	X	X	X	X	X	X	X	X	X	X	–	X	–	–	–	–	–	–
Dispense study drug 	–	X	X	X	X	X	X	X	X	X	X	X	–	–	–	–	–	–	–	–
Collection of study drug vials	–	–	X	X	X	X	X	X	X	X	X	X	X	–	–	–	–	–	–	–
Start consent process for INS-312								X m												

Protocol Amendment #3 version: 22 February 2016

*This protocol is solely for the purpose of communicating information about the investigational drug between Insmmed Incorporated and study personnel. Information is not to be reproduced, abstracted or used for sharing of information for any other purpose, whatsoever, except with the written permission of Insmmed Incorporated.*

Confidential

**Note:** At visits where study drug is administered, all patient-reported outcomes, 6MWT, Physical Exam should be performed before study drug administration.

**Note:** Culture conversion is defined to occur when the first of 3 consecutive monthly sputum cultures are MAC negative. All NTM treatment will stop when a subject has completed 12 months of treatment starting from their first of 3 negative cultures when they were defined as a ‘converter’.

Abbreviations: AE, adverse event; CRP, C-reactive protein; CT, computed tomography; ECG, electrocardiogram; EOS, End of Study; EOT, End of Treatment; ED-5D-3L, EuroQol 5D; FEF(25-75%), forced expiratory flow at 25-75% of FVC; FEV1, forced expiratory volume in 1 second; FVC, forced vital capacity; PK, pharmacokinetic; SGRQ, St. George’s Respiratory Questionnaire.

- a Home Healthcare visits may be available for sites with IRB/EC approval to conduct Home Healthcare visits, and for qualifying subjects who may have difficulty attending clinic visits.

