## **Sub-Study Design**

Eligible subjects must be enrolled into the INS-212 study. At randomization (Day 1), any subject who has signed the informed consent for this chest CT Scan Sub-Study will participate; there is no maximum number of subjects that can participate. At the latest, the informed consent and the subject's Baseline chest CT scan must be collected no later than 2 weeks after the subject's first dose of LAI or multi-drug regimen in the INS-212 study. A prior chest CT scan may be used as a subject's Baseline measure if this CT scan was obtained within 6 months from the subjects Day 1 study visit. All subjects in this chest CT Scan Sub-Study will have their follow-up chest CT scan on the (EOT) visit ( $\pm 14$  days) provided the last chest CT scan was not obtained within the prior 6 months. High resolution CT scan is preferred, if available.

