### **Sub-Study Objectives**

1. To compare assessments of radiographs, read by a trained medical professional, from Baseline (Day 1) in CT scans at EOT in Japanese subjects from sites in Japan
2. To assess the safety of LAI by CT scans (at 6 month intervals) in subjects from sites in Japan

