### **Sub-Study Design**

Eligible subjects must be enrolled into INS-212: A Randomized, Open-Label, Multicenter Study of Liposomal Amikacin for Inhalation (LAI) in Adult Patients with Nontuberculous Mycobacterial (NTM) Lung Infections Caused by *Mycobacterium avium* complex (MAC) That are Refractory to Treatment. The informed consent for this Japan specific CT Scan Sub-Study is included in the informed consent for the main study. All Japanese subjects in Japan will participate in this sub-study. There is no maximum number of subjects that can participate. The subject's Baseline chest CT scan must be collected no later than 2 weeks after the subject's first dose of LAI or multi-drug regimen in the INS-212 study. A prior chest CT scan may be used as a subject's Baseline measure if this CT scan was obtained within 6 months from the subject's Baseline (Day) 1 study visit in the INS-212 study. All subjects will have CT scans at their Months 6, 12, and EOT visits, and at 18 and 24 months after EOT.

Protocol Amendment #3 version: 22 February 2016

*This protocol is solely for the purpose of communicating information about the investigational drug between Insmid Incorporated and study personnel. Information is not to be reproduced, abstracted or used for sharing of information for any other purpose, whatsoever, except with the written permission of Insmid Incorporated.*

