**Table 14-4 Schedule of Events for INS-212 Japan Specific CT Scan Sub-Study**

INS-212 Japan Specific CT Scan Sub-Study							
	Screening	Baseline (Day 1)	Month 6	Month 12	EOT	Month 18	Month 24
	(V1)	(V2)	(V8)	(V11)	(V13)	–	–
Visit Window		(-6 months to +14 Days)	(±3 days)	(±3 days)	(±14 days)	(±14 days)	(±14 days)
Informed Consent a	X	-	–	–	–	–	–
CT Scan of Chest		X b	X	X	X b	X	X

a In Japan, all subjects will participate in the CT scan sub-study. Informed consent for this sub-study is included in the informed consent of INS-212 main study.  
b A prior chest CT scan may be used as a subject's Baseline (Day 1) measurement if this CT scan was obtained within 6 months from the subject's Baseline (Day 1) visit. Subjects will have their follow-up chest CT scan at the EOT visit provided the last chest CT scan was not obtained within the prior 6 months. High resolution CT scan is preferred, if available.

Protocol Amendment #3 version: 22 February 2016

*This protocol is solely for the purpose of communicating information about the investigational drug between Insmmed Incorporated and study personnel. Information is not to be reproduced, abstracted or used for sharing of information for any other purpose, whatsoever, except with the written permission of Insmmed Incorporated.*

Confidential

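### Both CT sub-studies accept a Baseline chest CT taken up to 14 days after the first dose, so the LAI arm's Baseline can already reflect LAI

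*Protocol*

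**What the plan says.** Timing of the Baseline scan:

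- Appendix 5 (Japan), Sub-Study Procedures: "The first chest CT scan should be performed at Day 1 or up to 14 day after first dose of LAI or multi-drug regimen". Its Sub-Study Design section agrees: "The subject's Baseline chest CT scan must be collected no later than 2 weeks after the subject's first dose of LAI or multi-drug regimen". Table 14-4 gives the window as minus "6 months to +14 Days".
- Appendix 4 (other sites), Sub-Study Design: "Baseline chest CT scan must be collected no later than 2 weeks after the subject's first dose of LAI or multi-drug regimen". Table 14-3 has the same window.
- Both appendices also accept a scan obtained in the previous 6 months.

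Other Day 1 assessments are held to a stricter order. The note to Table 3-1 says that "all patient-reported outcomes, 6MWT, Physical Exam should be performed before study drug administration". Audiology (Table 3-1, footnote g), spirometry (Section 6.2) and blood samples (Section 7.2.7.1) must also precede dosing.

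Use of the scan: Section 9.6.3 analyses CT change at EOT by ANCOVA with the Baseline measure as covariate. Both appendices have each later scan rated against the one before it. Japan has a further objective: "To assess the safety of LAI by CT scans (at 6 month intervals) in subjects from sites in Japan".

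End of treatment: both appendices allow the EOT scan within 14 days either side of EOT. Non-converters and subjects who relapsed by Month 6 leave at Month 8/EOT and may qualify for open-label LAI in Study INS-312 (Section 3.1; Table 3-1, footnote l). The protocol gives no date for the first INS-312 dose and no rule placing the scan before it.

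**The concern.** A Baseline should be measured before randomized treatment can act on it. Both arms start or continue a multi-drug regimen on Day 1, so a scan taken in the following fortnight exposes both arms alike to that regimen. LAI is given to one arm only. A post-dose Baseline can therefore contain a treatment effect in the LAI arm that has no counterpart among controls.

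Two uses of the scan then suffer. The ANCOVA adjusts for a value that treatment may have altered, and the first follow-up rating is made against that value. The protocol gives some reason to think early effects possible: Section 5.3 says local respiratory events became less frequent with continued use in prior LAI studies, and Section 8.3 lists allergic alveolitis, bronchospasm and hemoptysis as events of special interest. It does not say whether or how often CT would show them. For the Japanese safety objective, a reference scan taken on drug is a weaker starting point than one taken before it.

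The EOT scan raises a related question: could a control leaving at Month 8 be scanned after starting LAI in INS-312?

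**Working it through.** The plan states no figure on this point, so there is none to reproduce. The check is day arithmetic, with 1 month = 30.44 days (365.25/12) and 6 months = 182.6 days.

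**1. LAI exposure before the Baseline scan**

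- Permitted range: 0 to 14 days in the LAI arm, none in controls.
- Share of an 8-month course: 14 / (8 × 30.44) = 14 / 243.5 = 5.7%.
- A converter's first negative culture falls at Months 1 to 4, so EOT falls at Months 13 to 16. Shares: 14 / 395.7 = 3.5% and 14 / 487.0 = 2.9%.
- Number affected: not given. Appendix 4 expects at least 60 subjects. If these split 2:1, 60 × 2/3 = 40 are on LAI, and anything from 0 to 40 could have a post-dose Baseline.

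**2. Which results use that scan**

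- Appendix 4 has one follow-up scan, at EOT, so the EOT rating is made directly against Baseline.
- In Japan the Month 6 scan is rated against Baseline and later scans against their predecessors. The direct effect falls on the Month 6 rating.
- The ANCOVA in Section 9.6.3 uses the Baseline measure as covariate.

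**3. Appendix 4: is an EOT scan due at Month 8?**

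It is due if 6 months have passed since the last scan.

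- Baseline on day 14 and a nominal Month 8 scan: 243.5 − 14 = 229.5 days.
- Shortest gap, with Month 8 assessment 28 days early (Section 3.1) and the scan 14 days before that: 243.5 − 28 − 14 − 14 = 187.5 days.

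Both exceed 182.6, so the scan is due, and its window runs to 14 days after exit. If INS-312 dosing began 0 to 14 days after exit (an assumption), an exiting control could have 0 to 14 days of LAI before it.

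**4. Appendix 5: is an EOT scan due?**

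Sub-Study Procedures and Table 14-4, footnote b, apply the 6-month condition, but every subject also has a Month 6 scan (±3 days).

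- Shortest gap from Month 6 to Month 8/EOT: 60.9 − 28 − 14 − 3 = 15.9 days.
- Longest gap: 60.9 + 7 + 14 + 3 = 84.9 days.
- Converters, from the Month 12 scan to EOT at Month 16: 4 × 30.44 = 121.8 days, or 121.8 + 14 + 3 = 138.8 with windows.

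All are below 182.6. Under the conditional rule, neither an exiting subject who had the Month 6 scan nor a converter who had the Month 12 scan is due an EOT scan. Appendix 5, Sub-Study Design, nevertheless lists an EOT scan for every subject without the condition.

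**The case against.** The 14-day limit is an outer bound. Appendix 4 places a new scan on Day 1, and any subject with a CT from the previous 6 months needs no new scan. The outcome is an exploratory, locally read, three-category rating. Adverse events are collected from the first dose, and findings of every scan, Baseline included, are entered in the eCRF. An early lung event therefore has other routes into the data, and a reader who inferred that early harm is hidden would go too far. All of this stands and limits the point, but none of it makes a post-dose scan a proper Baseline.

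A reader might also infer that the timing rule always shrinks the difference between arms. It need not. An early LAI-related change that later cleared could be rated as improvement and favour LAI, and an LAI effect in a control's EOT scan could act either way. Direction depends on whether the early effect is harmful or beneficial, transient or lasting.

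On the EOT scan, Section 6.7 lists CT among EOT-visit procedures, to be done within 5 days of the scheduled visit. Section 5.12 bars anyone who leaves the study before Month 6 from INS-312. The introductions to both CT appendices describe the interest as converters who stay on treatment, although the endpoints are not restricted to them. The INS-312 protocol is not available and may itself order these steps. Control exposure before an EOT scan is therefore a possibility left open, not something the documents show.

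**Conclusion.** The Baseline point holds in both sub-studies. The protocol permits up to about two weeks of LAI before a newly acquired Baseline CT, which can put a post-treatment value into the LAI arm's reference scan and covariate. How many scans are affected, and the direction and size of any bias, cannot be determined from the document. The primary endpoint, sample size and alpha are untouched. Severity is minor.

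The EOT point holds only for Appendix 4, and only on the assumption that INS-312 dosing could start within 14 days of exit. It would be tempting to extend it to Japan. There, the 6-month condition and the Month 6 scan normally remove the Month 8/EOT scan, so the question arises only if the Month 6 scan was missed or the unconditional sentence is followed. That sentence and the conditional rule contradict each other, and they must be reconciled.

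**What to change.** - **Appendix 5.** Require the Baseline CT between 6 months before Day 1 and the first dose. Remove the 14-day allowance from Sub-Study Design, Sub-Study Procedures and Table 14-4. The cost is small, because CT consent is part of the main consent at Screening.
- **Appendix 4.** Require the Baseline CT after eligibility is confirmed and before the first dose, in the text and Table 14-3. Two other rules must change with it: the bar on a sub-study CT during Screening (Sub-Study Procedures) and the requirement that consent follow randomization (Table 14-3, footnote a). Left as they are, they would force consent, scan and first dose into the Day 1 visit for anyone without a prior CT.
- **Both appendices.** Label any later first scan as post-dose and do not use it as Baseline in the main CT analysis.
- **Appendix 4, EOT.** For subjects entering INS-312, require the EOT CT before any INS-312 dose. This costs almost nothing.
- **Appendix 5, EOT.** Reconcile the unconditional EOT scan in Sub-Study Design with the 6-month condition in Sub-Study Procedures and Table 14-4, footnote b.

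The first and fourth changes, with the matching Appendix 4 Baseline rule, cut the permitted LAI exposure before the scans concerned from at most 14 days to none. The cost is amendment wording and tighter scan booking. The main downside is that some Appendix 4 subjects without a prior CT may have no valid Baseline.

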## **6.7 END OF TREATMENT – UP TO MONTH 16 (VISIT 13) DURING THE RANDOMIZED, TREATMENT PHASE**

All of the following should be performed or obtained within 5 days of the scheduled visit:

- obtain 12-lead ECG (see [Section 7.2.5](#))
- administer SGRQ (see [Section 7.3.1](#))
- administer EQ-5D-3L (see [Section 7.3.2](#))
- collect information on healthcare resource utilization
- administer physical examination, including vital signs and pulse oximetry. (see [Section 7.2.2](#) and [Section 7.2.3](#))
- administer 6MWT (see [Section 7.2.1](#))
- administer audiology test (see [Section 7.2.9](#))
- obtain CT chest scan if part of CT Scan Sub-Study and no less than 6 months have elapsed since the previous CT scan was performed (see [Section 7.3.4](#), [APPENDIX 4](#))
- (Japan only) at Month 16, obtain CT chest scan as part of Japan specific CT Scan Sub-Study (see [APPENDIX 45](#))
- solicit concomitant medications (see [Section 7.2.8](#))
- assess AEs (see [Section 8](#))
- collect sputum specimen for microbiological assessment (see [Section 7.1.1](#))
- collect blood and urine specimens for clinical chemistry, hematology, and urinalysis testing and, for women of child-bearing, a urine pregnancy test (see [Section 7.2.7](#))
- collect blood (serum) specimen for biomarker assessment (CRP and IL-6) (see [Section 7.2.7](#))
- dispense sputum collection containers (see [Section 7.2.7](#))
- collect previously dispensed study drug vials from subject

Protocol Amendment #3 version: 22 February 2016

*This protocol is solely for the purpose of communicating information about the investigational drug between Insmmed Incorporated and study personnel. Information is not to be reproduced, abstracted or used for sharing of information for any other purpose, whatsoever, except with the written permission of Insmmed Incorporated.*

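### Japan CT sub-study: one rule for the EOT scan cannot be met on schedule and contradicts two others, and the only structured grade is not against Baseline

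*Protocol*

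**What the plan says.** All statements are in the protocol.

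- **Conditional scan.** Appendix 5, Sub-Study Procedures, takes the scans after Baseline at "Months 6, 12, EOT months (if at least 6 months have elapsed since the previous CT scan"). Table 14-4 marks the EOT scan with footnote b, which allows it "provided the last chest CT scan was not obtained within the prior 6 months".
- **Unconditional scan.** Appendix 5, Sub-Study Design: "All subjects will have CT scans at their Months 6, 12, and EOT visits". Section 6.7, for Japan: "at Month 16, obtain CT chest scan as part of Japan specific CT Scan Sub-Study". Neither sentence carries the 6-month condition.
- **Objective and endpoint.** The first objective in Appendix 5 compares CT assessments between Baseline (Day 1) and EOT. The first endpoint is "Radiological changes in CT scan at EOT in the LAI arm compared to multi-drug regimen alone, where appropriate".
- **What is recorded.** Scans are read locally, with a description of findings for each one. For every scan after Baseline, "An overall assessment of improved, worsening, or no change from previous scan will be reported".
- **Missing EOT scan.** Section 9.6.3 uses the prior scan in the analysis when no scan is done at EOT.

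**The concern.** The condition copies the wording of the global CT sub-study (Table 3-1, footnote i). That sub-study scans only at Baseline and EOT (Table 14-3), so a 6-month gap is normal there. Appendix 5 keeps the condition but adds scans at Months 6 and 12, and these shorten the gap.

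Two things are at stake. First, a Japanese site cannot follow all four statements, and sites may resolve the conflict differently. Some subjects would then have a true EOT scan and others a carried-forward one. Second, whichever rule is followed, the recorded grade describes change since the previous scan, while the objective asks for change since Baseline. The length of that step depends on whether the subject converted, and conversion is what the trial expects treatment to alter.

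**Working it through.** **Inputs**

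- Conversion is 3 consecutive monthly negative cultures within the first 6 months (Section 4.6), so the first negative falls at Month 1, 2, 3 or 4.
- EOT for converters is 12 months after that first negative (Section 3.1).
- Non-converters leave at Month 8 (Section 3.1).
- The Month 12 window is ±5 days in Section 6.5 but ±3 days in Table 14-4. The Month 6 scan window is ±3 days and the EOT scan window ±14 days (Table 14-4).
- One month is taken as 30.4375 days, so 6 months = 6 × 30.4375 = 182.6 days.

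**The plan's own figure first.** Latest first negative at Month 4, plus 12 months, gives EOT at Month 16. This matches the maximum of 16 months of treatment in Section 3.6.2.

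**Gap before EOT, converters.** Gap = EOT month − 12, with EOT at Month 13 to 16, so 1, 2, 3 or 4 months. Widest case, with the Month 12 scan 5 days early and the EOT scan 14 days late: 4 × 30.4375 + 5 + 14 = 140.8 days, or 4.6 months. With the ±3 days of Table 14-4: 121.75 + 3 + 14 = 138.8 days.

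**Gap before EOT, non-converters.** Gap = 8 − 6 = 2 months. Widest case: 2 × 30.4375 + 3 + 14 = 77.9 days, or 2.6 months.

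Both maxima are below 182.6 days, so the visit windows do not rescue the condition.

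**Who could still meet it.** Only subjects off schedule. A converter who misses the Month 12 scan has a gap of 7 to 10 months (EOT at Month 13 to 16, minus 6). A subject who stops at Month d, before the Month 6 scan, qualifies if a historic Baseline scan was taken at least 6 − d months before Day 1.

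**What the structured grade covers for a subject on schedule**

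| Reading | Converter | Non-converter |
|---|---|---|
| Condition applied; prior scan used (Section 9.6.3) | Month 12 against Month 6 | Month 6 against Baseline |
| EOT scan taken (Sub-Study Design, Section 6.7) | EOT against Month 12, a step of 1 to 4 months | Month 8 against Month 6, a step of 2 months |

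No converter cell spans Baseline to the analysed scan. For non-converters this happens only under the first reading, and there it ends at Month 6 rather than EOT. In each row the interval differs between converters and non-converters.

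**The case against.** **The endpoint is not lost.** A reader might infer that the EOT endpoint cannot be measured. The documents do not support that. Two passages require the scan outright, and if it is not taken Section 9.6.3 supplies the prior scan. For converters that is a late on-treatment scan 1 to 4 months before EOT. This objection stands. The fault is a contradiction and a mislabelled time point.

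**The rule is not uniform.** A reader might also take the 6-month condition as the protocol's only rule. It is one of two conflicting rules, and off-schedule subjects can satisfy it. Section 6.7 does send Japanese sites to Appendix 5, but that does not settle the matter, because the design and procedures texts of Appendix 5 disagree with each other.

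**No split by arm follows from the planning rates.** It is tempting to say that 20% of LAI and 5% of control subjects (Section 9.1) would be graded over Months 6 to 12 and the rest from Baseline to Month 6. That does not hold. The 20% is a floor. Converters who relapse by Month 6 leave at Month 8. At Japanese sites, stopping study drug means leaving the study (Section 5.12), so some subjects may have no Month 6 scan.

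**The analysed variable may not be the grade.** Section 9.6.3 plans an ANCOVA with the Baseline measure as covariate, findings are described for every scan, and all scans must be available to the sponsor. The derivation may be set out in an SAP that is not shown. So a comparison with Baseline remains possible by re-reading. It is still true that the one structured item Appendix 5 collects on change is relative to the previous scan. This part does not depend on the 6-month condition and would remain if every EOT scan were taken.

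**Low stakes.** The endpoint is exploratory (Section 3.4, item 10) and qualified by the phrase on appropriateness. The second Japanese objective, safety at 6-month intervals, is served by the Month 6 and Month 12 scans. This is also correct.

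**Conclusion.** The point holds as a minor one. The conditional rule in Sub-Study Procedures and in Table 14-4 footnote b excludes the EOT scan for every subject on schedule, with a largest gap of about 141 days for converters and 78 days for non-converters against about 183 days required. It contradicts Sub-Study Design and Section 6.7. If it is applied, the result labelled EOT is a Month 12 or Month 6 scan carried forward. Under either reading, the structured grade is against the previous scan and does not deliver the Baseline-to-EOT change in the first objective.

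This rests on three assumptions: Month 6 and Month 12 scans are taken as scheduled, non-converters have their EOT at Month 8, and the carry-forward rule of Section 9.6.3 applies to the Japanese sub-study as it does to the global one. The primary analysis is not affected.

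**What to change.** 1. Reconcile Section 6.7, the Sub-Study Design and Sub-Study Procedures texts of Appendix 5, and Table 14-4 footnote b on whether an EOT scan is taken. Which rule stands is for the sponsor to decide.
2. Have the existing local reader grade each post-Baseline scan against Baseline as well as against the previous scan, and use the Baseline grade for the first endpoint.
3. If the 6-month condition stands, describe the endpoint as change from Baseline to the last on-treatment scan, and report the month of that scan by arm.
4. A between-arm comparison at Month 6 may be added as supportive, since that scan is scheduled before conversion status decides who stays. It need not replace the endpoint: Appendix 5 is interested in subjects who converted and continued on treatment, and a Month 6 comparison alone would drop that question.

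The cost is revised wording and one extra recorded grade per scan. Items 2 to 4 add no scans.

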### **9.6.3 Exploratory Endpoint Analyses**

The change in 6MWT distance at Month 6 for converters compared with non-converters overall for ITT population, within LAI plus a multi-drug regimen, within the multi-drug regimen alone, the change in BMI at Month 6 for LAI plus a multi-drug regimen compared with a multi-drug regimen alone, and the changes in chest CT scan at EOT for LAI plus a multi-drug regimen compared with a multi-drug regimen alone in a sub-set of subjects will be analyzed using the ANCOVA models with the comparison arm (converters vs. non-converters or the treatment arm) and the randomization strata as factors, and the corresponding Baseline measure as a covariate. If a CT scan is not performed at EOT for any subject, then prior CT scan will be used in the analysis.

The change from Baseline (Day 1) to Month 6 and EOT in the EQ-5D-3L patient reported health outcomes will be analyzed for the ITT population similarly using the same MMRM method as the analysis of the change from Baseline to EOT in 6MWT distance. Kaplan-Meier estimates for the distribution of time to death will be constructed by treatment arm. The treatment comparison will be made using the stratified log rank test for the ITT population. Incidence of new MAC strains will be summarized by treatment arms.

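### In the Japan CT sub-study, scans are graded against the previous scan, so a converter's last rating does not measure the change from Baseline that objective 1 asks for

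*Protocol*

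**What the plan says.** Appendix 5 gives the Japan sub-study two objectives. The first compares readings "from Baseline (Day 1) in CT scans at EOT in Japanese subjects from sites in Japan", and the matching endpoint is "Radiological changes in CT scan at EOT in the LAI arm compared to multi-drug regimen alone, where appropriate". The second is "To assess the safety of LAI by CT scans (at 6 month intervals) in subjects from sites in Japan".

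For each scan, Sub-Study Procedures in Appendix 5 orders a written description of findings and one graded item: "An overall assessment of improved, worsening, or no change from previous scan will be reported for all scans" after the Baseline scan. The same sentence stands in Appendix 4, whose schedule (Table 14-3) has only a Baseline and an EOT scan.

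Appendix 5 is not consistent about the EOT scan. Sub-Study Design lists it without a condition: "All subjects will have CT scans at their Months 6, 12, and EOT visits, and at 18 and 24 months after EOT". Sub-Study Procedures attaches one: "Additional CT scans will be obtained at their Months 6, 12, EOT months (if at least 6 months have elapsed since the previous CT scan" (the bracket closes there). Footnote b of Table 14-4 sets the same kind of 6-month condition.

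For the analysis, Section 9.6.3 says: "If a CT scan is not performed at EOT for any subject, then prior CT scan will be used in the analysis". CT change is to be analysed by ANCOVA with treatment arm and randomization strata as factors "and the corresponding Baseline measure as a covariate".

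**The concern.** The question asked is net change since Baseline. The grade collected is change since the last scan. With two scans these are the same thing. With scans at Baseline, Month 6, Month 12 and possibly EOT they are not.

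A converter whose scan improves by Month 6 and then holds is graded unchanged at Month 12, although the net change from Baseline is an improvement. The first six months, in which conversion occurs by definition, fall outside that subject's last rating. Non-converters leave by Month 8 and have no Month 12 scan, so the period behind the last rating depends on conversion status, which the trial expects treatment to alter. The reference scan is fixed when the reading is recorded, so a later analysis cannot supply a Baseline-referenced grade without a re-read.

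**Working it through.** **Inputs.** Conversion is three consecutive monthly negative cultures within the first 6 months (Section 4.6). A converter's EOT is 12 months after the first of those negatives, and a non-converter's last visit is Month 8 at the latest (Sections 3.1 and 6.7). Treatment lasts at most 16 months (Section 3.6.2). Planned conversion is 20% with LAI and 5% in control (Section 9.1).

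**Step 1: timing of EOT.** If the first negative is at Month f, the third is at f + 2, and f + 2 ≤ 6 gives f = 1, 2, 3 or 4. EOT = f + 12 = Month 13, 14, 15 or 16. The largest value reproduces the protocol's 16-month maximum.

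**Step 2: is an EOT scan due under the 6-month condition?** Take a month as 30.4375 days, so 6 months = 182.6 days. The EOT scan window is 14 days (Table 14-4). The visit windows are 5 days at Month 12 and 3 days at Month 6 (Table 3-1).
- Converters: EOT is 1 to 4 months after the Month 12 scan. Longest gap = 4 × 30.4375 + 14 + 5 = 140.8 days.
- Non-converters: EOT is 8 − 6 = 2 months after the Month 6 scan. Longest gap = 2 × 30.4375 + 14 + 3 = 77.9 days.

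Both are below 182.6 days. With scans on schedule no EOT scan is due in either group, and Section 9.6.3 sends the analysis to the prior scan.

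**Step 3: period covered by the analysed rating.**

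| Reading of Appendix 5 | Converters | Non-converters |
|---|---|---|
| EOT scan conditional (Sub-Study Procedures, Table 14-4) | Month 6 to 12 | Baseline to Month 6 |
| EOT scan unconditional (Sub-Study Design) | Month 12 to Months 13–16 | Month 6 to 8 |

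Only one of the four cells starts at Baseline, and it ends at Month 6.

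**Step 4: can net change be rebuilt from the chain?** Take the pair (Month 6 against Baseline, Month 12 against Month 6), with three grades each, so 3 × 3 = 9 pairs. Taking a grade of unchanged at face value:
- The last grade equals net change in 5 pairs: improved–improved, unchanged–improved, unchanged–unchanged, unchanged–worse, worse–worse.
- The last grade differs from net change in 2 pairs: improved–unchanged (net improved) and worse–unchanged (net worse).
- Net change cannot be determined in 2 pairs: improved–worse and worse–improved.

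**Step 5: share by arm.** Under the conditional reading the Month 6 to 12 rating applies to about 20% of LAI and 5% of control. The other 80% and 95% are rated from Baseline to Month 6.

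**The case against.** The strongest reply is that the protocol never names the grade as the endpoint variable. A description is recorded for every scan, Baseline included, and an ANCOVA with a Baseline covariate implies a measure taken on each scan, which a change rating cannot provide. A statistical analysis plan, not at hand here, could code the descriptions. This stands in part. The protocol defines no such measure, and the one graded reading it orders does not match its objective.

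Other points stand and limit the concern:
- All ratings are kept, so improved followed by unchanged can be read as a net improvement. Only 2 of 9 pairs are undeterminable. But no rule for combining ratings is given, and Section 9.6.3 points to a single scan.
- Scans are stored, so a re-read against Baseline is possible. None is specified.
- Under the conditional reading most subjects are rated from Baseline, although at Month 6 rather than EOT.
- The previous-scan grade suits the six-month safety objective.

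A reader might infer more than the documents support:
- **Bias toward no effect.** This would need the radiological benefit to be complete by Month 6. The protocol says nothing on its timing, and the Appendix 5 introduction is interested in subjects who convert and stay on treatment, a period that Months 6 to 12 partly cover.
- **Every Japan rating covers only the last few months.** That follows only from the unconditional text.
- **Appendix 4 has the same defect.** An intervening scan matters there only if an EOT scan is still due. If the intervening scan is too recent for that, it is itself analysed, and its predecessor is Baseline.

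**Conclusion.** The point holds for the Japan sub-study and is minor. Under either reading of the EOT scan rule, a converter's last rating does not start at Baseline, so it does not measure objective 1. Under the conditional reading this concerns about 20% of LAI and 5% of control, and the period rated differs by arm through conversion. Under the unconditional reading no EOT rating starts at Baseline in either group. The direction and size of any bias cannot be derived from the protocol.

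This assumes that Month 6 and 12 scans are on schedule, that the trial-wide planning rates apply in Japan, and that converters reach Month 12. Those who relapse by Month 6 leave at Month 8 and fall with the non-converters. Early discontinuation or a missed scan gives other intervals. The endpoint is exploratory and the primary analysis is unaffected.

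**What to change.** In Appendix 5, Sub-Study Procedures, add one eCRF item: each scan after Baseline is also graded improved, worse or unchanged against the subject's own Baseline scan. Add the same item in Appendix 4 for consistency. Name it as the graded rating for Japan endpoint 1 and for exploratory endpoint 10. Keep the previous-scan grade for the six-month safety objective in Japan.

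Separately, reconcile Sub-Study Design with Sub-Study Procedures and Table 14-4 on whether the EOT scan is conditional. Section 9.6.3 should also be checked, because a grade of change has no Baseline value to use as the ANCOVA covariate.

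The cost is one more eCRF item, with the same scans and the same local reader. The change aligns the starting point only. Follow-up length would still differ: Baseline to Month 12 against Baseline to Month 6 under the conditional text, or Baseline to Months 13–16 against Baseline to Month 8 under the unconditional text, because non-converters leave by Month 8.
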